1.3 Design

The proposed design is a pragmatic two-arm trial. Children randomised to the intervention group will start Otovent treatment immediately, whilst treatment in the control group will be delayed until the end of a 3 month comparison period. Children in both trial groups will undergo tympanometry at baseline, 1 and 3 months but usual clinical care will not be otherwise constrained. In the intervention group, children with normal tympanometry in both ears at 1 month will discontinue autoinflation whilst those with persisting OME will be encouraged to continue for up to two further months.

The intervention will be offered to control children with residual tympanic dysfunction at the end of the 3 month comparison period as we believe it will substantially increase recruitment to the study. The main study period up to 3 months will evaluate the additional benefit over usual care of a standardised purpose manufactured autoinflation device (Otovent) in improving OME, in school aged children in primary care, as assessed by a more objective method (tympanometric resolution) than history, at both1 and 3 months.

We will assess cost effectiveness at the end of the randomised 3 month active monitoring period as the health economic main outcome in terms of costs and QALYs, and will also include resolution of OME in the shorter term (1 month), and use an extrapolated scenario analysis including the data from the 6 month audit for longer term projections of costs.

A period of three months active monitoring (watchful waiting) has been chosen as it is best current practice. Good clinical practice also requires that children deemed as severe or protracted at the outset may need to be referred for surgery immediately and excluded from the trial; it is envisaged that this group will be very small.

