The observed transience of improved pressure changes in the middle ear from the autoinflation method has been questioned as a sufficiently adequate explanation for any therapeutic mechanism, with what appears to be singular theoretical reliance on restoration of tubal function (for a condition of mixed aetiology). The beneficial effects of changes in gas composition e.g. of small rises in oxygen tension in the middle ear (associated with improved middle ear ventilation over time), may also be theoretically important however, and may fit with ongoing research into the role of hypoxia in some genotypes, in particular the MRC Jeff mouse genetic model of otitis media. Autoinflation may also improve natural drainage by dislodging any mucus plugs blocking the Eustachian tubes etc. The clinical trial evidence to date supports a distinct therapeutic effect from autoinflation in compliant groups, however unclear the theoretical mechanism (this also holds true for OME causation in general). A clinical trial applied earlier in the natural history in primary rather than secondary care (where effusions have developed to be more mucoid and tenacious) is *prima facie* more likely to be effective using this aerating technique and in preventing sequelae. Along with severity, relevant effect modifiers for this method may include child age/head size, and compliance frequency. Season was not found to be an effect modifier in a primary care study.

Otovent is already available on NHS FP10 prescriptions (cost £7.20 per month for adults, with children exempt). If the short-term cure suggested in the Cochrane review were realisable in everyday practice (see power calculation), our hypothesised estimate of the potential effect on health and clinical practice is a 70% reduction in antibiotic prescribing, a 30% reduction in GP re-consultations, and 50% reduction in hospital referrals with insertion of grommets.^{4,11}

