The main analysis will be on an intention to treat basis i.e. as randomised, to reduce attrition bias and improve generalisability of the sample. We will seek to minimise any loss to follow up in all groups. A per protocol secondary analysis to estimate effects due to compliance will also be performed. Because autoinflation is also available over the counter, possible contamination bias may occur due to use in the control arm, but will be explicitly dealt with by asking patients guardians prior to randomisation to agree not to buy and use autoinflation devices for 3 months if randomised to the control arm. This effect should also be minimised by ensuring good patient/guardian and practice communication and education. Furthermore all patients may receive autoinflation by the end of 3 months as part of the trial if they so choose. At 3 months the guardians will be asked if Otovent was purchased independently to the study, or indeed if any other autoinflation device was used or tried. We will also remind patients and their families that currently Otovent is only recommended in children after they have first seen their own GP, and should be obtained on an FP10 prescription not obtained over the counter. We will ask research nurses to double-check if any "additional" Otovent was inadvertently prescribed in controls during the first 3 month period.

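### The control-arm undertaking is worded around buying a device and does not expressly cover one obtained on prescription, the route that the same section names to all families

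*Protocol*

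**What the plan says.** Section 3.5 names one route of contamination: "Because autoinflation is also available over the counter, possible contamination bias may occur due to use in the control arm". The remedy is that guardians, before randomisation, "agree not to buy and use autoinflation devices for 3 months if randomised to the control arm". Three further measures follow in the same paragraph.

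- Education: "This effect should also be minimised by ensuring good patient/guardian and practice communication and education". Its content is not given.
- A reminder: "We will also remind patients and their families that currently Otovent is only recommended in children after they have first seen their own GP", and that it "should be obtained on an FP10 prescription not obtained over the counter". The reminder is addressed to patients and families in general, with no restriction by arm or by time.
- Detection: "At 3 months the guardians will be asked if Otovent was purchased independently to the study", or whether some other autoinflation device was used or tried. Research nurses also check whether Otovent was inadvertently prescribed to controls in the first 3 months.

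Elsewhere, section 2.3 states that "Otovent is already available on NHS FP10 prescriptions" and that children are exempt from the charge. Section 1.3 delays treatment in the control group until the end of the 3-month comparison, then says that "usual clinical care will not be otherwise constrained". Section 3.2.3 describes control care as the practice's usual care, unaffected by the study. The primary outcome is tympanometric resolution at 1 month (section 7.1), analysed by intention to treat (sections 3.5 and 8.2).

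**The concern.** The undertaking closes the purchase route. The reminder then names the prescription route as the proper one, and section 2.3 says that this route costs a child's family nothing. A control family that sees its GP, receives a prescription and uses the device in the first weeks has broken neither statement as written. Section 3.5 plainly regards such use as unwanted, yet the sentence that families agree to does not say so, and no instruction tells practices whether a prescription to a control child counts as usual care or as contamination.

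At stake is the primary contrast. Any control child who benefits from the device before the 1-month tympanogram still counts as a control under intention to treat, which pulls the comparison towards no effect. The question to guardians comes two months after that outcome and is worded so that prescribed or borrowed Otovent fits neither of its parts.

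**Working it through.** **1. The statements side by side**

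| Route to a device in a control child | Undertaking (3.5) | Reminder (3.5) | Guardian question at 3 months (3.5) | Other capture |
|---|---|---|---|---|
| Otovent bought over the counter | covered | discouraged | asked | not needed |
| Another autoinflation device | covered if bought | not addressed | asked | not needed |
| Otovent on prescription | not expressly covered | named as the proper source | not expressly asked | nurse check, after the event; notes review (8.3) |
| Otovent borrowed | not expressly covered | not addressed | not expressly asked | none stated |

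The undertaking and the question are weakest on the prescription route, which the reminder points to, and on borrowed devices.

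**2. What could date early use**

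Section 3.2.3 gives parents a daily check sheet that includes details of any treatment used. Section 7.2 collects diaries and questionnaires at 1 month. Section 8.3 plans a case-note review for all children over the 3 months. These may date some use, and a GP prescription would ordinarily be dated in the notes. None is stated to ask controls about autoinflation.

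**3. The plan's own sample size**

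Inputs from section 8.1: control cure p1 = 0.45, odds ratio 2.4, alpha 5% (taken as two-sided), power 90%, 125 per arm, 15% loss.

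- Odds in the intervention arm = 2.4 × 0.45/0.55 = 1.964, so p2 = 1.964/2.964 = 0.6626.
- n per arm = [1.96 √(2 p̄ q̄) + 1.2816 √(p1 q1 + p2 q2)]² / (p2 − p1)², where p̄ is the mean of p1 and p2 and q = 1 − p.
- With p2 rounded to 0.66, this gives 116 per arm. With the continuity correction it gives 125, hence 250 in total, and 250/0.85 = 294.1, rounded up to 295.

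The stated 250 and 295 are therefore reproduced. No allowance for control-arm use is among the stated inputs.

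**4. Illustration of dilution**

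Suppose a share c of controls uses the device before 1 month with full benefit. The control cure rate becomes p1(c) = 0.45 + c × (p2 − 0.45). For c = 10% and p2 = 0.6626, p1(c) = 0.45 + 0.1 × 0.2126 = 0.4713, and the difference falls from 21.3 to 19.1 points.

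Power at n = 125 per arm without continuity correction is Φ{[(p2 − p1) √n − 1.96 √(2 p̄ q̄)] / √(p1 q1 + p2 q2)}, with p1(c) in place of p1.

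| c (assumed) | Difference, points (p2 = 0.6626) | Odds ratio | Power, p2 = 0.6626 | Power, p2 = 0.66 | Power, p2 = 0.66, continuity-corrected |
|---|---|---|---|---|---|
| 0 | 21.3 | 2.40 | 92.7% | 92.1% | 90% |
| 5% | 20.2 | 2.30 | 90.1% | 89.3% | 87% |
| 10% | 19.1 | 2.20 | 86.7% | 85.9% | 83% |
| 20% | 17.0 | 2.02 | 78.0% | 77.0% | 73% |

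The dilution depends on c multiplied by the share of the benefit obtained. If users gained only half the effect, 20% use would do what the 10% row shows: 0.45 + 0.2 × 0.5 × 0.2126 = 0.4713.

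**The case against.** The best case for the protocol reads the paragraph as a whole. The reminder sits among the anti-contamination measures and discourages over-the-counter purchase. The nurse check treats a prescription to a control as inadvertent, so its unwanted status is implied. Section 1.3 delays control treatment to 3 months, and its remark that care is not otherwise constrained comes after that delay. Practices are to be educated, the GPs are principal investigators who could act as a gate, and the promise of the device at 3 months reduces the incentive to seek it early. All of this stands as evidence of intent. It does not put the prescription route into the undertaking or remove it from what control families are told, and the content of the education is unspecified.

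A reader might infer three stronger things that the documents do not support.

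- *That the protocol directs controls to the device.* It does not; it names a source while discouraging another.
- *That early control use could never be dated.* The check sheet, the 1-month forms and the notes review may date some of it.
- *That contamination would be large.* The protocol gives no rate. Full benefit is also generous, because section 3.4 defines the intervention as device plus training and support, which a control with a prescribed pack would not receive from the trial. Sharing between siblings in opposite arms is conceivable, but no section mentions it.

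**Conclusion.** The point holds as a gap in wording and in capture. The undertaking does not expressly cover a prescribed device, the reminder names that route to families in both arms during the comparison, and the 3-month question does not expressly pick up prescribed or borrowed Otovent. The protocol does not tell practices how its view of such prescribing as inadvertent fits with unconstrained usual care.

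The direction of any effect is clear: effective use by controls before 1 month dilutes the primary comparison. The size is not known. The power figures rest on assumed rates, full benefit to users, 125 analysed per arm and a two-sided 5% test. On that basis, 10% use costs about 6 to 7 points of power and 20% use about 15 to 17, depending on rounding and continuity correction. The sample size calculation itself is not in question.

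**What to change.** 1. Reconcile the undertaking and the reminder in section 3.5 with sections 1.3 and 3.2.3 on whether a prescribed device in a control child is contamination or usual care, and tell the practices. If it is contamination, as section 3.5 implies, word the undertaking to cover a device from any source until the 3-month assessment.
2. For control families, keep the message against over-the-counter purchase but leave out the pointer to FP10 until the 3-month assessment is complete.
3. Add one item for controls to the existing 1-month and 3-month questionnaires: any autoinflation device used, its source and the start date. Use the notes review already planned in section 8.3 to identify prescriptions dated before the 1-month tympanogram.

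The cost is the rewording of one undertaking and one reminder, a line to practices and one extra questionnaire item. If the undertaking is widened, the control condition is slightly more constrained than now, in the direction that section 3.5 already intends.

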3.6 Inclusion criteria

- Aged 4-11 years and attending school at the time of the first planned tympanometric screen. (To be
 able to reliably perform the technique and have a greater theoretical chance of cure).
- A relevant notes recorded history of recent and or recurrent otitis media symptoms (defined as within
 the last year) or ear related problems in the previous year (e.g. suspected hearing loss, slow speech
 development etc.-audit terms specified); or a guardian denotes a concern in one or more OME
 related symptom domains* on the screening invitation letter symptom check list (in the targeted 4 to 7
 years of age and seasonal high risk of OME groups).
- Tympanometric confirmation in a child of at least one B tympanogram (using the modified Jerger classification). This has a ~90% Positive Predictive Value of an effusion being present. i.e. cases of unilateral or bilateral OME.

*Symptom lists have been developed from those reported in the GNOME trial, important OM8-30 symptom variables, and the recently updated Deafness Research UK 2009 parent information sheet about glue-ear, that also highlights typical symptoms *e.g.* speech concerns, mis-hears what is said, appears inattentive etc.

3.7 Exclusion criteria

- Children who need early referral as judged clinically, to include those known rarer cases with high risk
 of recurrence: Down's, cleft palate, Kartagener's, Primary Ciliary Dyskinesia, immunodeficiency
 states etc.
- 4 year old children not attending school at the time of screening, or children deemed by the nurse unable to comply with the technique of autoinflation.
- At study entry, children with a grommet already in place in an ear drum, or where the child has been referred or listed for ear surgery.
- Latex allergy (balloons are latex)
- A recent nose bleed in the past 3 weeks or more than one episode of nose bleeding over the past 6 months

3.8 Withdrawals

In accordance with recommended ethics practice guardians and children will be free to withdraw from the study at any time without affecting their usual high standard of medical care. Children in the autoinflation group will be advised to stop the intervention in the instance of any suspected related (expected or unexpected) serious adverse events. All children that do cease the intervention will be followed up (unless the parents withdraw consent) as this study an intention to treat analysis.

4. ETHICAL ARRANGEMENTS

This trial aims specifically to improve child health for this group of children and to establish the best non-surgical treatment for children with OME. Children are the main "consumer" group suffering from OME and its protracted effects, so adult studies (with a different aetiology and natural history) are inappropriate. As this trial will randomly allocate an additional treatment with preliminary evidence of effectiveness for the patient's condition as an adjunct to standard care, there will be no compromise of their care from the NHS. Trial support for clinical care with improved diagnostic monitoring should ensure exemplary clinical management during the NICE recommended active monitoring period (3 months).¹¹

A qualified research nurse, used to working with children, will be given specific training in the trial protocol and will be provided with the trial manual. They will conduct all the trial procedures e.g. interviews and assessments, provide instructions etc. which will be minimally invasive (e.g. otoscopy, micro- tympanometry, web hearing disability test, study questionnaires). All trial staff (Research Nurses, Principal Investigators, the Chief Investigator and Trial Manager) will attend an approved ICH-Good Clinical Practice training session if they have not received training within the year prior to the main trial commencement date.

Children will only be involved after full informed consent is given. In accordance with National Research Ethics Service (NRES) guidance 6-11 year olds will be asked to give their assent after their parent/guardian has given consent. For the younger children (4-5 year olds) only the parent/guardian will be asked for consent, and no assent will be sought from these children. If a child refuses to participate or carry on, once consented into the trial their decision will always be respected. No pressure will be exerted on a child or their parent/guardian to participate nor will they receive financial benefit other than modestly priced book tokens for completing the diaries. There are several approved trial information sheets: a detailed one for the parents/guardians; one for 6-11 year olds and one for 4-5 year olds.

The NRES application form and trial documentation for the pilot and the main study were submitted to Southampton and South West Hampshire REC and received a favourable opinion in August 2009. As Otovent is a CE marked medical device, MHRA approval is not required. As for the pilot study site-specific Information forms have already been submitted and obtained for each pilot site contributing to the main study to cover local Site-Specific Assessment and for R&D requirements.

5. RISKS AND ANTICIPATED BENEFITS

As with all trials there is always a degree of risk to participants, however in this particular trial the risks are estimated to be extremely small. No side effects have been reported from current trials. The main theoretical side effect is an increase in upper respiratory infection due to air pressures generated in the nasal cavity equivalent to being submerged under 2-3 foot of water somehow spreading infected mucus up the Eustachian tubes. No such increase in infection rate has been noted in the trials so far and in fact the incidence of respiratory tract infection was observed to be higher in the control group in the only previous British study.²³

The fact that fluid behind the ear on tympanometry is found less commonly in treated groups in most trials to date also means that ear infections are likely to be less when using the device. The ICH-GCP guidelines for definitions of adverse events/reactions will be followed, and all adverse events/reactions will be recorded. The co-ordinating centre's standard operating procedure for safety reporting in studies not involving an investigational medicinal product will be fully complied with, including reporting of all serious adverse events (e.g. any unplanned hospitalisation) to the sponsor immediately, and as will all related unexpected serious adverse events. In addition to any expedited reports, annual safety reports will be submitted to the main REC.

Placebo treatment is not planned at all in this children's study. All children/guardian participants will be offered the intervention after 3 months of the study if they were not initially randomised to the +autoinflation arm, and the fluid/effusion has not gone away by that time.

Using the combinations of:"natural cure+ standard care +/- any treatment effect from adjunctive use of the device," constitutes possibly the best primary care approach currently available to evaluate. On the basis of the NICE 2009 guideline which recommends active monitoring for OME for 3 months, and states "autoinflation may be beneficial in older children". Although standard care will be fully detailed in the study there is no evidence for any significant effect of any of the commonly used treatments on tympanometric resolution. The level of trial care and aftercare will be thorough and, as proposed, will meet high standards.

5.1 Informing potential trial participants of possible benefits and known risks

In addition to the methods described under recruitment procedures, which will allow potential participants ample time to consider consent, we will provide a clear, appropriate and relevant information sheet for both children and guardians to consider the potential benefits and possible risks. With supplementary summary information available if requested (e.g. NICE summary¹¹ Cochrane review²⁰ etc)

6. RESEARCH GOVERNANCE

The sponsor is the University of Southampton. Agreements will be put in place between the sponsor and all participating sites outlining the roles and responsibilities of all parties. The trial will comply with the Data Protection Act 1998 and will comply with local issues required at each site. Non negligent harm will be covered by the University of Southampton and negligent harm will be covered by each GP practice's insurance Consumers will be involved at each stage of this trial - design, trial documents (*e.g.* consent forms, information sheets), conduct, analysis and reporting. The trial will be co-adopted by the Primary Care Research Network and the Medicines for Children Network (MCRN) and would become part of the latter's General Paediatrics Clinical Study Group (CSG). Following the MCRN's adoption of the GNOME study, the research team has had strong links with this network and this CSG from their inception.

A Trial Management Group (TMG) will meet regularly to review progress. A Data Monitoring Committee (DMC) will be established with a statistician and 1-2 other members who are independent of the study centre.

The DMC will review the data and any adverse events/reactions identified by GPs. A Trial Steering Committee (TSC) will be established with an independent chair and will meet regularly to ensure the trial is running to target, budget and time, and to resolve any issues incurred. A lay person will be invited to join the Trial Steering Committee to assist with the trial conduct, analysis and reporting.

6.1 Regulation compliance

This study will be conducted in accordance with the Research Governance Framework for Health and Social Care; the ICH-GCP guidelines and the updated version of the Declaration of Helsinki

6.2 Retention of trial documentation

Trial documentation in any study involving minors should be archived until 3 years after the youngest subject reaches 18 years old. Therefore all trial documentation for this study will be archived for 20 years to fulfil the above requirement in accordance with Good Research Practice (MRC 2005)

